Pilot and Feasibility Study 2: The RISE Study also served to pilot-test some of the procedures proposed for PPG II. This study included interview, phlebotomy, and MRI-PET preoperatively and interview, phlebotomy, LP and MRI-PET at one month post-operatively. No TMS was conducted in this study. As of January 16, 2019, we have successfully completed 38 post-operative LPs and 77 MRIs for this study, without any complications or adverse effects.

B3. DESCRIPTION OF RESEARCH PROTOCOL

A. Study Design – Overview, Methods, Procedures

A.1. Brief overview of the study:

This study is based on our previous Program Project (PPG) that created the original SAGES I cohort (SAGES, Protocol: 2009P-000262). During the first PPG, we enrolled a cohort of >560 older surgical patients (SAGES I) and documented: an accelerated trajectory of long-term cognitive decline following delirium and important risk markers for delirium related to inflammation, structural disconnectivity, and impairment in global cognitive performance. These important findings have paved the way for us to move forward to extend our pathophysiologic understanding through innovative probes of brain vulnerability. This project will deepen our exploration of pathophysiologic pathways potentially contributing to delirium and its associated cognitive decline. We will examine the role of inflammation; Alzheimer's disease (AD) biomarkers (cerebrospinal fluid, CSF, and neuroimaging markers); and measures of *brain plasticity/connectivity* (transcranial magnetic stimulation and evoked potentials). These approaches were chosen based on their innovation, potential to probe vulnerability, and ability to advance our mechanistic understanding. We will also identify and validate predictors of complicated delirium, i.e., delirium associated with long-term cognitive decline. All of these studies will utilize both the original SAGES I cohort, and a new prospectively enrolled cohort, SAGES II, which will include CSF sampling obtained prior to spinal anesthesia if possible (some patients will get general anesthesia and for some with spinal anesthesia we may not get CSF).

A.2. Overall Study Design.

This observational study seeks to better describe the complex relationship of *delirium, dementia, and brain vulnerability* by exploring a different aspect of vulnerability involving two different prospective observational cohorts: Successful Aging after Elective Surgery I (SAGES I) and SAGES II.

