A.4.9. Hospital assessments: The purpose of the hospital assessment is to monitor daily for development of delirium and to assess precipitating factors. We anticipate that all patients in the surgical group will be hospitalized. Automatic systems will be in place to notify the principal investigator immediately whenever an enrolled study patient is admitted to the BIDMC or BWH. Upon admission, the patient will be seen by the study team in the hospital (in-person or remotely via telephone or videoconference using an IRB approved platform like zoom or Starleaf), and will undergo daily 10-15 minute interviews including a cognitive screen, digit span test, CAM, DSI, MDAS ratings, and new delirium severity measures. Precipitating factors (e.g., infections, immobilization, surgical procedures, post-surgical complications) will be assessed by interview and review of the medical record using standardized, validated methods applied in our previous studies. The initial hospitalization during the study period will be considered the index hospitalization. The timing of follow-up will begin from the point of discharge. For study purposes readmission within 24 hours is considered a continuation of the hospital stay. Our study team is highly experienced in conducting such interviews in hospitalized persons, which will assist in assuring retention, as well as avoiding any interference with ongoing

medical care. If a patient is discharged on the day of surgery, we will conduct the POD 1 and/or POD 2 hospital interview in patient's discharge location or on the phone.

A.4.10. Post-hospitalization follow-up assessments: Several types of follow-up assessments will be conducted, as detailed below. These are all timed in relationship to the discharge date of the index hospitalization. Intercurrent illnesses and re-hospitalizations will be assessed at each follow-up time-point. If patients are hospitalized at the time of a scheduled follow-up assessment, we will wait for one month from hospital discharge to complete the follow-up assessment, to minimize the effects of acute illness on cognitive functioning. Some attrition is anticipated at each follow-up time point (due to mortality and losses to follow-up in this older population). These attrition rates are accounted for in all power calculations below.

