Aim 2. To evaluate associations of delirium and CSF AD biomarkers (sampled near 4 year follow-up) in a probability sample from SAGES I (N=128): (1) 64 patients who developed delirium during the initial hospitalization; (2) 64 who did not develop delirium during initial or subsequent hospitalizations. Statistical power and sample size considerations. Hypothesis 2a: The analytic question can be simplified as detecting a difference on a continuous dependent variable--the individually varying time slope--across delirium and non-delirium groups. With two groups of size 64, Lehr's equation⁵⁷ informs that with assumptions of 5% and 20% type-I and type-II error rates, the minimum detectable effect size is d = 0.5 standardized units. This is close to the observed effect we have reported out to 3 years in our parent study cohort (d = 0.48),²² and feasible to detect with our MSD approach.⁵⁶ Hypothesis 2b: Since we expect to find stronger effects with longer follow-up from this analysis, we anticipate adequate power to address this hypothesis. Utilizing a two-sample t-test for the difference in slopes across biomarker groups results in a minimal detectable effect size of d= 0.53, with an overall positivity rate of 34% (30% in 109 cognitively normal and 60% in 19 with MCI), which should be feasible to detect based on our prior studies. Hypothesis 2c: Since purely descriptive, power is not calculated.

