Aim 3. To examine the relationship of novel SiMoA assays of t-tau and NFL in plasma obtained prior to surgery in SAGES I (n=148) with delirium incidence/severity and LTCD following delirium. Sample size and statistical power considerations. Hypothesis 3a: With a sample size of 148, the minimum detectable correlation coefficient is r = .25 (using single sample two-sided type-I error level of 5% and type-II error level of 20%). A single sample, one-sided test that the observed correlation is greater than r = .50 is associated with 5% type-I error and 80% power. Given our pilot yielding r=.61 and the literature r=0.52-0.89,^{58,59} we anticipate adequate power. Hypothesis 3b: Here we assume similar rates of biomarker positivity as in Aim 2. Given a minimum detectable rate ratio of exp(4/sqrt(n)), where n is the harmonic mean of the sample with and without abnormal levels of t-tau and NFL⁶⁰ and levels of type-I and type-II error of 5% and 20%, respectively, as biomarker positivity ranges from 30 to 60%, our minimum detectable odds ratio for the association of biomarker positivity and delirium will range from 2.8 to 3.7, describing areas under the ROC curve (AUC) of 0.62 to 0.66, which are medium to large effects.⁶¹ For delirium severity, the minimum detectable effect size varies from d = 0.50 to 0.55 as biomarker positivity ranges from 30 to 60%. These effects are feasible to detect given prior work showing A β_{42} and tau positivity rates of 70-80% in delirium vs. 40-50% in nondelirium, and odds ratios for delirium given biomarker positivity of 2.1-3.2.62 Hypothesis 3c: The analytic question can be simplified as detecting a difference on a continuous dependent variable -- the individually varying time slope--across biomarker abnormal vs. normal groups. With a balanced

distribution of biomarker abnormality and with two groups of size 64, Lehr's equation⁵⁷ assuming 5% and 20% type-I and type-II error rates, yields a minimum detectable effect size ranging from d = 0.50 to 0.55 standardized units as biomarker positivity ranges from 30% and 60%. These effects appear feasible to detect given our prior studies and the published literature.^{22,62}

Project 2

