Aim 3 Analyses: Hypothesis 3a posits that CSF and plasma t-tau and NFL will have Pearson correlation of at least r = .50. This analysis will be approached with correlational methods. Variables will be evaluated and transformed as appropriate prior to estimating a correlation coefficient. Hypothesis 3b seeks to test if abnormal levels of t-tau and NFL from stored plasma at baseline will be associated with a higher risk of developing delirium and greater delirium severity. This will be tested with logistic regression (delirium occurrence) and linear regression (delirium severity). The control variables will be the same as above. Missing data will be addressed using multiple imputation (50 imputations) and the chained equations approach.⁷² Hypothesis 3c seeks to test if patients with abnormal levels of t-tau and NFL from stored plasma at baseline will have a faster rate of LTCD (over a minimum of 8 years) compared to those without abnormal biomarker levels. This hypothesis will be evaluated using generalized linear mixed effect modeling as described above for H1b and as previously conducted in our prior publications.²² The outcome is a composite measure of cognitive functioning^{55,73} and the main exposures are biomarker abnormality, time and their interaction. A faster rate of LTCD among those with delirium is revealed by a significant interaction between delirium group and the long-term time trend. Hypothesis 2c. The analytic approach is similar to H1b, and posits that the two effects are at least partially independent in the generalized linear effects models (i.e., the effect of biomarker positivity is only partially mediated by delirium). Since purely descriptive, power is not calculated.

Project 2

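### Project 1 power text: H3a names no alternative and has about 61% power at the pilot correlation, H3b's detectable odds ratios are not reproduced and do not support its feasibility claim, and Aims 1-2 deduct nothing for attrition or missing CSF

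*Protocol*

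**What the plan says.** **H3a (B.1.3, Project 1, Aim 3).** "With a sample size of 148, the minimum detectable correlation coefficient is r = .25" against zero, two-sided. Then: "A single sample, one-sided test that the observed correlation is greater than r = .50 is associated with 5% type-I error and 80% power". The support offered is "Given our pilot yielding r=.61 and the literature r=0.52-0.89", from which adequate power is inferred. B.2.3 states the hypothesis itself: "CSF and plasma t-tau and NFL will have Pearson correlation of at least r = .50". Table 1 labels this aim exploratory.

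**H3b (same aim).** The formula is "Given a minimum detectable rate ratio of exp(4/sqrt(n)), where n is the harmonic mean of the sample with and without abnormal levels". For positivity of 30-60% it reports detectable odds ratios of 2.8 to 3.7. These are called feasible on two grounds: prior biomarker positivity of 70-80% with delirium versus 40-50% without, and prior odds ratios of 2.1-3.2.

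**Aims 1 and 2.** Aim 1 gives d = 0.28 to 0.33 for 400 patients at 25-50% positivity, against a benchmark of d = 0.48. Aim 2 reads "With two groups of size 64, Lehr's equation" and gives d = 0.5 for H2a. H2b gives d = 0.53 at 34% positivity.

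**Attrition and CSF.** Section A.4.10, on SAGES II follow-up, says: "These attrition rates are accounted for in all power calculations below". Section B.1 says of all cohorts that the computations take cumulative attrition into account. Section A.1 warns that "some patients will get general anesthesia and for some with spinal anesthesia we may not get CSF", and A.2 offers amyloid PET to SELECT patients who cannot have a lumbar puncture. Section B.1.2 says the power was worked out for 128 and 400 and expects the increase to 148 and 460 to exceed it.

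**The concern.** A power figure against a non-zero null means little until the alternative is named. A reader who sees 80% followed directly by the pilot value will join the two, and the pilot value does not give 80%. In H3b, detectable effects that mostly exceed the effects cited in their support do not show feasibility. In Aims 1-2, the text says losses are included while the arithmetic leaves no room for them, and the protocol itself expects some patients to have no CSF. At stake is how a null biomarker result is read: whether the study was equipped to see the effects that it cites.

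**Working it through.** **H3a.** Inputs: null .50, one-sided 5%, n = 148, pilot .61, literature .52-.89 (all B.1.3).

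Power = Φ[(atanh r₁ − atanh .50)·√(n−3) − 1.645].

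- At r = .61: atanh .61 = 0.7089 and atanh .50 = 0.5493. The difference 0.1596 × √145 (12.04) = 1.922. Then 1.922 − 1.645 = 0.277, so power is 0.609. A 30,000-run simulation gave 0.606.
- At r = .52: power 0.09. At r = .70: 0.986. At r = .89: about 1.
- r for 80%: tanh[0.5493 + (1.645 + 0.842)/12.04] = .639.
- Pairs for 80% at r = .61: (2.487/0.1596)² + 3, about 246.
- With fewer pairs (assumed counts) at r = .61: 0.53 with 120 and 0.47 with 100. PET yields no CSF tau or NFL, so a patient scanned instead of punctured is lost to this test.

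A side check on the r = .25 against zero: tanh[(1.960 + 0.842)/√(n−3)] is .229 at n = 148 and .245 at n = 128. The stated value fits 128.

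**H3b.** First the plan's own formula. At N = 128 and 30% positivity, the harmonic mean is 2 × 0.3 × 0.7 × 128 = 53.76, and exp(4/√53.76) = 1.73. Converted to an odds ratio at 50% delirium overall, this is 3.49. Across 30-60% positivity the range is 2.64-3.49 at N = 128 and 2.48-3.15 at N = 148. Neither is 2.8-3.7.

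Next a direct two-sided 5% comparison of two proportions (pooled variance under the null), with 50% delirium overall and positivity of 30-60%:

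| | N = 128 | N = 148 |
|---|---|---|
| Detectable odds ratio, 80% power | 2.72-3.01 | 2.54-2.78 |
| Power at odds ratio 2.1 | 0.47-0.55 | 0.53-0.61 |
| Power at odds ratio 3.2 | 0.84-0.90 | 0.89-0.94 |

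Example: N = 148, 50% positivity, odds ratio 2.1 gives proportions .592 and .408. Power = Φ[(0.1834 − 1.96 × 0.0822)/0.0808] = Φ(0.276) = 0.61.

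**Aims 1-2.** Detectable d by Lehr = 4/√(harmonic mean of group sizes).

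- Aim 1, N = 400: 4/√200 = 0.283 at 50% positivity and 4/√150 = 0.327 at 25%. Stated: 0.28-0.33.
- H2a, 64 per group: 4/√64 = 0.500. Stated: 0.5.
- H2b, 34% of 128: 4/√57.45 = 0.528. Stated: 0.53.

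Each figure is met with every patient present, so no loss was deducted. The later increase gives headroom of 1 − 400/460 = 13.0% and 1 − 128/148 = 13.5%.

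Aim 1 by the share of 460 with both CSF and follow-up (yields assumed, since the protocol gives none):

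| Yield | N | Detectable d, 50% to 25% positivity |
|---|---|---|
| 100% | 460 | 0.264-0.305 |
| 80% | 368 | 0.295-0.341 |
| 70% | 322 | 0.315-0.364 |
| 50% | 230 | 0.373-0.431 |

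For d = 0.48 to become undetectable, the harmonic mean must fall below (4/0.48)² = 69.4. That is N of about 139 (30% of 460) at 50% positivity, or 185 (40%) at 25%.

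H2a power at d = 0.48 (normal approximation): 0.83 with 148, 0.79 with 133 (10% loss), 0.74 with 118 (20% loss). The loss rates are assumed.

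**The case against.** A reader might infer that the protocol claims 80% power at r = .61 and is simply wrong. It does not: no alternative is attached to the 80%, and the value that gives 80%, about .64, lies inside the cited literature range. The aim is also labelled exploratory, so it does not carry the sample size. What stands is the missing alternative and the inference drawn from .61.

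A reader might also infer that H3b is generally underpowered. The stated 2.8-3.7 is pessimistic: at 148 the direct figure is lower, and power is high at the top of the cited odds ratios. The positivity contrast cited alongside implies odds ratios from 2.3 (70% v 50%) to 6.0 (80% v 40%). H3b uses stored plasma, so missing CSF does not touch it. What stands is that the printed range is not reproduced and does not support the conclusion beside it.

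The most tempting reading is that Aims 1-2 fail to deliver their power. The documents do not show that. They give no Project 1 attrition or CSF-failure rate, and the larger targets absorb moderate loss. H2a has delirium group as its exposure and needs no CSF. PET can stand in for amyloid status, though not for tau or NFL. Mixed models and multiple imputation keep patients with partial follow-up in the analysis. In-hospital delirium is not exposed to follow-up loss. The A.4.10 sentence concerns SAGES II only. The general statement in B.1 does cover Aim 2, however, and it does not match the arithmetic.

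**Conclusion.** The point holds in three limited parts.

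1. H3a's 80% has no stated alternative, and the pilot value offered in support does not reach it. This assumes bivariate normality and all 148 pairs; fewer pairs lower the power further.
2. H3b's detectable range is not reproduced, and most of the odds ratios cited for it fall below that range as printed. The recalculation assumes the sampled 50% delirium and is unadjusted for covariates.
3. The attrition statements are untrue for Project 1 Aims 1-2, and the expectation of exceeding the stated power holds only while combined loss stays under about 13%. At an assumed 10% loss the stated effects are still met; at 20% they are not. The yields are assumptions, and Aim 1's conclusion against its own benchmark survives all those shown.

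Nothing here shows that the sample size is inadequate. The printed figures should be corrected before anyone relies on them.

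**What to change.** - **H3a:** state that 80% power corresponds to a true r of about .64 with 148 pairs and that power is about 61% at .61, or recast this exploratory hypothesis as an estimated correlation with a confidence interval. Give the expected number of CSF-plasma pairs.
- **H3b:** replace 2.8-3.7 with about 2.5-2.8 at 148 (50% delirium, 30-60% positivity). Report power of about 53-61% at an odds ratio of 2.1 and 89-94% at 3.2.
- **Attrition:** amend A.4.10 and B.1 to say that Project 1 Aims 1-2 were computed without deduction. Qualify B.1.2 by saying that the increase covers about 13% combined loss, and add the Aim 1 yield table.

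The cost is a revision of the power text. Some figures become less favourable and H3b's become more so. No patients, procedures or analyses need be added; recasting H3a would change only how its result is reported.

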Aim 1: To use SOMAscan proteomics to discover new inflammatory proteins associated with delirium and LTCD in both plasma and CSF, and then validate these proteins in an independent sample. Sample Size Justification: In our SOMAscan pilot study of 18 matched pairs, we identified YKL40 as one of several strong biomarkers. We computed the estimate of power based upon the observed effect size of YKL40. The mean of paired differences was 125252 RFU (relative fluorescence unit), and standard deviation 64071. For clinical significance, we would like to detect an effect size as small as 1/3 this observed difference. For H1A plasma, with 60 matched pairs, we will have a power of 0.98 to observe this effect size with type-I error of 0.05. For H1A CSF, with 40 matched pairs and similar effect size threshold, the power will be 0.93. For H1B plasma, we will dichotomize the 60 delirium cases into those experiencing faster and slower rates of LTCD. Based on our published finding that patients with faster LTCD tend to have more severe delirium ⁶³, we expect that the effect size will be larger for this outcome, and set the clinically significant threshold at one-half of the observed difference with YKL40. With these assumptions, the calculated power will be 0.99. For H1B CSF, with 20 matched pairs and similar assumptions, the power will be 0.94. Finally, for H1C, we plan to measure selected proteins in plasma and CSF across the SAGES II cohort of 460 patients. We estimate that 24%, or 96 patients will develop delirium. Based on our previous CRP POD2 findings, we assume an estimated relative risk of 2.0 for a biomarker effect for delirium incidence ⁶⁴. To account for the impact of confounders in the multivariable model, we conservatively reduce this expected odds ratio effect size to 1.6. With type-I error at 0.05, we obtain a power estimate of 0.8. Thus, we anticipate good power for the H1C validation analyses.

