Aim 2: To use mass cytometry (CyTOF) to characterize circulating immune cells associated with delirium and LTCD, and then validate these findings in an independent sample. Sample Size Justification: We base the power analysis for this aim on the pilot study of 7 non-delirious patients with percent of cell types CD45+CD11c+CD14+monocytes to total number of cells, measured at PREOP and POD1. The median of the paired differences was 10.15 with range 10.07-15.19, and the mean was 10.62 with SD of 6.55. We plan to use 40 matched pairs. Since this observed mean paired difference is for the surgery effect and not the delirium effect, we use 50% of this difference as the clinically significant delirium effect. We also assume that the signal to noise ratio is similar for the delirium effect, thus SD is expected to be 6.55. With these assumptions, we obtain a power of 0.98 for H2A. For H2B, focused on LTCD, assuming a larger effect size of 60% of the observed surgical effect, we obtain a power estimate of 0.94. For H2C, the validation sample with 40 matched pairs from SAGES II, we consider a cell surface marker with a relative risk of 1.6 with delirium compared to no delirium. With type-I error at 0.05, we obtain a power estimate of 0.82.

Aim 3: To measure CRP and the Walston inflammatory index in banked plasma, and freshly collected plasma and CSF, from a probability sample of 148 SAGES I participants (SAGES I SELECT). Sample Size Justification: For Aim 3, we have 148 subjects, probability sampled for delirium (74 with and 74 without) and frequency matched for age and baseline GCP. The predictors are the measured levels of plasma inflammatory markers, and CSF inflammatory and AD biomarkers. The outcomes are delirium and LTCD. We use a relative risk of 1.5 as the threshold of clinical significance, and a type-I error of 0.05, and calculate 0.84 power for delirium and 0.80 for LTCD. Thus, we have very good power for this Aim.

Project 3

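### Project 2 Aim 2: the printed pilot range, mean and SD cannot all describe the same seven values, although the mean and SD feed the H2A and H2B powers, and H2B's 0.94 cannot be confirmed as written

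*Protocol*

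**What the plan says.** All of this is in Protocol B.1.3, Project 2, unless noted.

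- **Source of the inputs (Aim 2).** "We base the power analysis for this aim on the pilot study of 7 non-delirious patients". The measure is a monocyte percentage before surgery and on postoperative day 1. The summary reads: "The median of the paired differences was 10.15 with range 10.07-15.19, and the mean was 10.62 with SD of 6.55".
- **H2A.** "We plan to use 40 matched pairs". The effect is half the pilot mean: "we use 50% of this difference as the clinically significant delirium effect". The SD is carried over: "We also assume that the signal to noise ratio is similar for the delirium effect, thus SD is expected to be 6.55". The result: "With these assumptions, we obtain a power of 0.98 for H2A".
- **H2B (LTCD).** The whole statement is: "assuming a larger effect size of 60% of the observed surgical effect, we obtain a power estimate of 0.94". It gives no number of patients or pairs, no layout and no test.
- **Nearest parallels (Aim 1).** For H1B plasma, "we will dichotomize the 60 delirium cases into those experiencing faster and slower rates of LTCD". For H1B CSF, the power of 0.94 is attached to 20 matched pairs.
- **Error rate.** B.1 sets a two-sided type-I error of 0.05 for the computations.

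**The concern.** An SD of 6.55 is larger than the whole printed interval, which is 15.19 - 10.07 = 5.12 wide. The mean of 10.62 also looks too low when nothing lies below 10.07 and one value is 15.19. If the interval is the minimum and maximum, the summary cannot have come from one set of seven numbers.

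The stake is the sample-size justification for this aim. Both effects are fractions of that mean and the SD is taken over unchanged, so an error in either passes straight into the 0.98 and the 0.94. The direction is unknown. For H2B there is a second problem: a reader who accepts the mean and SD still cannot tell what calculation produced 0.94.

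**Working it through.** **1. Can the pilot figures coexist?** Inputs: n = 7, minimum 10.07, median 10.15, maximum 15.19.

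- *Lowest possible mean.* Put three values at 10.07, three (including the median) at 10.15 and one at 15.19: (3 × 10.07 + 3 × 10.15 + 15.19)/7 = 75.85/7 = 10.84. Printed: 10.62.
- *Highest possible SD.* Ignoring the median, the extreme is a 3/4 split between the two ends: √[5.12² × (3 × 4/7)/6] = √7.49 = 2.74. With the median held at 10.15 it is 2.73. Printed: 6.55, about 2.4 times the cap.

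**2. Would one misprinted limit explain it?**

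- *Minimum wrong only.* Keep mean 10.62 (sum 74.34), median 10.15 and maximum 15.19. The most spread-out set is -1.68, 10.15, 10.15, 10.15, 15.19, 15.19, 15.19, with SD 5.98. This is still below 6.55.
- *Maximum wrong only.* Keep mean 10.62, median 10.15 and minimum 10.07. The largest value can be at most 74.34 - 3 × 10.07 - 3 × 10.15 = 13.68, and the SD is then 1.35.
- *Interval is an interquartile range.* The set -1.46, 10.07, 10.10, 10.15, 10.20, 15.19, 20.09 has its second and sixth values at 10.07 and 15.19, median 10.15, mean 74.34/7 = 10.62 and SD √(257.46/6) = 6.55. All the printed figures then hold.

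**3. H2A with the printed inputs.** Effect 0.5 × 10.62 = 5.31; d = 5.31/6.55 = 0.811; 40 pairs; two-sided 0.05.

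| Calculation | Power (stated 0.98) |
|---|---|
| Paired t, 40 pairs | 0.999 |
| Sign-test approximation, 40 pairs | 0.983 |
| Paired t, 40 pairs, SD 6.55 × √2 (6.55 read as one patient's change, partners uncorrelated) | 0.94 |

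The sign-test approximation is Φ(d√(2n/π) - 1.96).

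**4. H2B with the printed inputs.** Effect 0.6 × 10.62 = 6.372; d = 6.372/6.55 = 0.973; two-sided 0.05. The n and layout are assumptions, because the protocol gives none.

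| Assumed layout and test | Power (stated 0.94) |
|---|---|
| 40 pairs, paired t | > 0.999 |
| 20 pairs, paired t | 0.985 |
| 20 pairs, Wilcoxon (simulated) | 0.98 |
| 20 pairs, sign-test approximation | 0.935 |
| 20 pairs, exact sign test | 0.90 |
| 20 v 20, two-sample t, SD 6.55 per group | 0.850 |
| 20 v 20, Mann-Whitney (simulated), SD 6.55 per group | 0.82 |
| 20 v 20, two-sample t, SD 6.55/√2 per group | 0.989 |

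No t-test version gives 0.94. Only the sign-test approximation comes within two points of it at the two-sided level. A one-sided normal approximation at 20 v 20 gives 0.924, but that departs from the two-sided rule in B.1.

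**5. Direction if the interval is right.** With an SD of 2.74 and the printed mean, H2A (40 pairs) and H2B (20 v 20) both exceed 0.999. Correcting the summary need not lower the powers.

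**The case against.** A reader might infer that H2B's true power is 0.85 and that 0.94 overstates it by nine points. The argument is that 40 matched pairs contain 40 delirium cases, that splitting these into faster and slower decliners gives about 20 v 20, and that those two groups are not each other's matches. This is a reasonable reading, but the documents do not support it as fact.

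- The split into faster and slower decliners is written for H1B plasma in Aim 1, not for H2B.
- The closest parallel, H1B CSF, has nearly the same standardised effect (125252/2/64071 = 0.977) and the same stated power of 0.94, and it is described as 20 matched pairs. On 20 pairs a paired t-test gives 0.985 for H2B, so 0.94 would be an understatement.
- The 0.85 takes 6.55, an SD of paired differences, as the SD within each group. At 6.55/√2 per group the same 20 v 20 comparison gives 0.989.
- Table 6 lists nonparametric inference for Project 2. A two-sided sign-test approximation lands within about half a point of five of its six paired figures: H1A plasma 0.981 (stated 0.98), H1B plasma 0.990 with 30 pairs assumed (0.99), H1B CSF 0.937 (0.94), H2A 0.983 (0.98) and H2B 0.935 with 20 pairs assumed (0.94). It misses H1A CSF, 0.908 against 0.93. This does not show what the sponsor did, but it leaves 0.94 with a possible origin.

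A second tempting inference is that the mean and SD are the wrong figures. That does not follow either. The interquartile-range example shows both could be right and only the label wrong. What survives these objections is the inconsistency itself and the missing specification of H2B.

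**Conclusion.** The pilot sentence is internally impossible as printed. A minimum of 10.07, median of 10.15 and maximum of 15.19 force a mean of at least 10.84 (printed 10.62) and an SD of at most 2.74 (printed 6.55). This needs no assumption beyond n = 7 and the ordinary meaning of a range. Which figure is wrong cannot be settled from the protocol, so neither the size nor the direction of any effect on the powers is known. If only the label is wrong, the mean, the SD and the powers derived from them are untouched.

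H2B's 0.94 is unverifiable rather than shown to be wrong. Given the printed mean and SD, two-sided t-tests with 20 pairs or 20 v 20 (SD 6.55 per group) span 0.85 to 0.985, and 0.935 is reached by one approximation the section does not name. H2A is less exposed: with the printed inputs it stays at 0.94 or above in each version in the H2A table. The aim is not invalidated, but its justification should be corrected.

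**What to change.** Go back to the seven pilot patients and recompute the median, the minimum and maximum (or the interquartile range, labelled as such), the mean and the SD. Correct the sentence in B.1.3, Project 2, Aim 2.

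Then restate the H2A and H2B powers from the corrected inputs. For H2B, give the number of patients or pairs, whether the comparison is paired or between independent faster and slower LTCD groups, which SD is used (of pair differences or within group), and the test. The figure 0.85 should not be written in as the H2B power unless the sponsor confirms the layout and SD behind it.

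The cost is one seven-value summary, two power calculations and a few lines of text. This correction does not itself require any change to sample size or procedures.
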